7.3.2. Method of Detecting AEs and SAEs

The method of recording, evaluating, and assessing causality of AE and SAE and the procedures for completing and transmitting SAE reports are provided in Appendix 3 (Section 9.3).

Care will be taken not to introduce bias when detecting AEs or SAEs. Open-ended and non-leading verbal questioning of the subject is the preferred method to inquire about AE occurrences.

7.3.3. Follow-up of AEs and SAEs

After the initial AE or SAE report, the Investigator is required to proactively follow each subject at subsequent visits/contacts. All SAEs, will be followed until resolution, stabilization, the event is otherwise explained, or the subject is lost to follow-up (as defined in Section 6.3). Further information on follow-up procedures is given in Appendix 3 (Section 9.3).

7.3.4. Regulatory Reporting Requirements for SAEs

- Prompt notification by the Investigator to the Sponsor or designee of an SAE is essential so that legal obligations and ethical responsibilities towards the safety of subjects and the safety of a study intervention under clinical investigation are met.

- The Sponsor has a legal responsibility to notify both the local regulatory authority and other regulatory agencies about the safety of a study intervention under clinical investigation. The Sponsor will comply with country-specific regulatory requirements relating to safety reporting to the regulatory authority, Institutional Review Boards (IRBs)/Independent Ethics Committees (IECs), and investigators.
- Investigator safety reports must be prepared for suspected unexpected serious adverse reactions (SUSARs) according to local regulatory requirements and Sponsor policy and forwarded to investigators as necessary.
- An Investigator who receives an Investigator safety report describing an SAE or other specific safety information (e.g., summary or listing of SAEs) from the Sponsor will review and then file it along with the IB and will notify the IRB/IEC, if appropriate according to local requirements.

7.3.5. Pregnancy

- Details of all pregnancies in female subjects and of female partners of male subjects will be collected after the start of study intervention and until 90 days after last dose of study intervention.
- If a pregnancy is reported, the Investigator should inform the Sponsor within 24 hours of learning of the pregnancy and should follow the procedures outlined in Appendix 4.
- Abnormal pregnancy outcomes (e.g., spontaneous abortion, fetal death, stillbirth, congenital anomalies, ectopic pregnancy) are considered SAEs.

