Cohorts 1 to 4 (weekly regimen): On Day -1, eligible subjects will be randomized (as described above) and be treated with SC injection of study intervention QW starting on Day 1 through Day 85; subjects will be domiciled at the Phase 1 unit from Day -1 (day before 1st dose) to Day 2 and from Day 28 (day before the 5th dose) to Day 30. Subjects will attend ambulatory clinic visits for dosing and evaluations per the SoA (Section 1.2.1, [Table 2](#)). On the Day 8, Day 15 and Day 22 ambulatory dosing visits, subjects will remain at the study site for observation for at least 2 hours post dose.

Cohorts 5 and 6 (every 2 weeks regimen): On Day -1, eligible subjects will be randomized (as described above) and be treated Q2W with SC injection of study intervention starting on Day 1 through Day 85; subjects will be domiciled at the Phase 1 unit from Day -1 (day before 1st dose) to Day 2 and from Day 28 (day before the 3rd dose) to Day 30. Subjects will attend ambulatory clinic visits for dosing and evaluations per the SOA (Section 1.2.1, [Table 4](#)). On the Day 15 ambulatory dosing visit, subjects will remain at the study site for observation for at least 2 hours post dose. On Days 64 and 78 subjects will be contacted by phone to inquire about AEs and concomitant medications.

Subjects in all cohorts will be followed up on Day 92 (1 week post last dose of study intervention) and Day 113, 4 weeks post last dose of study intervention (End of Study visit). Subjects who are found to be ADA positive at the end of study visit will be followed for 3-5 months after this visit or until stable or declining as deemed by the Medical Monitor.

Assessments during the study period will be done as specified in the Schedule of Activities (SoA; Table 2 for Cohorts 1-4 and Table 4 for Cohorts 5-6).

For each subject, the total duration of study participation will be up to 172 days (24.5 weeks) excluding the potential dose interruption due to the COVID-19 pandemic:

Screening period:	≤ 60 days (8.5 weeks)
Treatment period:	84 days (12 weeks)
Follow-up period	28 days (4 weeks)

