7.3.1. Time Period and Frequency for Collecting AE and SAE Information

All AEs and SAEs will be as specified in the SoAs (Table 2 for Cohorts 1-4, Table 4 for Cohorts 5-6, and Table 6 for Cohort 7).

Table 8 below summarizes the different reporting periods for AEs, SAEs, and events to monitor. Events to monitor are defined in Section 9.3.3.

Table 8 Adverse Event Reporting Periods

Type of Event	Adverse Event	Serious Adverse Event	Events to monitor with study intervention
Reporting period	From consent until 28 days after last dose of study intervention	From consent until 28 days after the last dose of study intervention	From consent until 28 days after the last dose of study intervention
Reporting Timelines to the Sponsor	Entered into the clinical database on an ongoing basis	Within 24 hours	Within 24 hours

All SAEs will be recorded and reported to the Sponsor or designee immediately and under no circumstance should this exceed 24 hours, as indicated in Appendix 3 (Section 9.3). The Investigator will submit any updated SAE data to the Sponsor or designee within 24 hours of it being available.

Investigators are not obligated to actively seek AEs or SAEs after conclusion of the study participation. However, if the Investigator learns of any SAE, including a death, at any time after a subject has been discharged from the study, and he/she considers the event to be reasonably related to the study intervention or study participation, the Investigator must promptly notify the Sponsor or designee.

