Contraceptive use by men or women should be consistent with local regulations regarding the methods of contraception for those participating in clinical studies.

Subjects should use highly effective, double contraception (both male and female partners) during the study and 30 days or 5 half-lives (whichever is longer) of study intervention.

Double contraception is defined as a condom with one of any of the following forms of birth control:

- Birth control pills (The Pill)
- Depot or injectable birth control
- Intrauterine Device (IUD)
- Birth Control Patch (e.g., Othro Evra)
- NuvaRing®
- vasectomy for men

Subjects may not donate sperm or oocytes during the study and for 30 days or 5 half-lives (whichever is longer) after last dose of study intervention.

Rhythm methods are not considered as highly effective methods of birth control. Subject abstinence for the duration of the study and 30 days or 5 half-lives (whichever is longer) after last dose of study intervention is acceptable if it is the subject's regular practice.

Collection of Pregnancy Information

Male subjects with partners who become pregnant

- The Investigator will attempt to collect pregnancy information on any male subject's female partner who becomes pregnant while the male subject is in this study. This applies only to male subjects who receive study intervention.
- After obtaining the necessary signed informed consent from the pregnant female partner directly, the Investigator will record pregnancy information on the appropriate form and submit it to the Sponsor within 24 hours of learning of the partner's pregnancy. The female partner will also be followed to determine the outcome of the pregnancy. Information on the status of the mother and child will be forwarded to the Sponsor. Generally, the follow-up will be no longer than 6 to 8 weeks following the estimated delivery date. Any termination of the pregnancy will be reported regardless of fetal status (presence or absence of anomalies) or indication for the procedure.

Female subjects who become pregnant

- Female subjects who become pregnant should discontinue treatment and be withdrawn from the study.
- The Investigator will collect pregnancy information on any female subject who becomes pregnant while participating in this study. Information will be recorded on the appropriate form and submitted to the Sponsor within 24 hours of learning of a

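### Protocol Section 7.3.5 collects pregnancies until 90 days after the last dose, but Appendix 4 describes collection only while the subject is in the study, so up to 62 of the 90 post-dose days may go uncovered.

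*Protocol*

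**What the plan says.** Three places in the protocol bear on when a pregnancy enters the safety record.

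- **Section 7.3.5 (Pregnancy)** covers female subjects and female partners of male subjects. Details are collected "after the start of study intervention and until 90 days after last dose of study intervention". A reported pregnancy is then handled under Appendix 4. The section also classes abnormal outcomes (spontaneous abortion, stillbirth, congenital anomaly and others) as SAEs.
- **Section 9.4 (Appendix 4)** describes collection for a "female partner who becomes pregnant while the male subject is in this study". For female subjects it says: "The Investigator will collect pregnancy information on any female subject who becomes pregnant while participating in this study". It states no number of days for either group. Once a pregnancy has been collected, it is followed to its outcome, generally up to 6 to 8 weeks past the estimated delivery date. After the study, pregnancy-related SAEs judged reasonably related are reported, but the investigator need not look for them in former subjects.
- **Section 7.3.1, Table 8** sets the SAE reporting period as "From consent until 28 days after the last dose of study intervention".

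Participation ends at the End of Study visit. In Part 1 weekly dosing runs "treated with SC injection of study intervention QW starting on Day 1 through Day 85" and the final visit is "Day 113, 4 weeks post last dose of study intervention (End of Study visit"). Section 4.2 gives the Part 2 equivalents: last dose on Day 134, End of Study on Day 162.

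**The concern.** The section that sets the collection window and the appendix that tells sites how to collect describe different periods. Two sites could each point to the protocol and collect different pregnancies.

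Female reproductive effects are a named potential risk (Section 2.3.1.3). Women of childbearing potential may enrol. The same section says that the single-dose study enrolled only women not of childbearing potential and is not informative for this risk. A pregnancy missed after treatment is therefore a gap in an area where the programme has little human information.

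No visit or call supports the 90-day rule. After the 28-day visit, routine contact stops. The exceptions are the extra antibody follow-up: in Part 1 for neutralizing-antibody-positive subjects per the Synopsis, or ADA-positive subjects per Section 3.2; in Part 2 for neutralizing-antibody-positive subjects per Section 4.2.

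**Working it through.** No sample-size or power formula applies; this is date arithmetic and a comparison of text.

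**1. Reproduce the stated follow-up period.** The Synopsis (Study Duration) gives 28 days for both parts. Follow-up = End of Study day − last-dose day.
- Part 1 (Section 3.2): 113 − 85 = 28 days.
- Part 2 (Section 4.2): 162 − 134 = 28 days.

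The stated figure reproduces.

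**2. Days inside Section 7.3.5 but after participation ends.** 90 − 28 = 62 days, in both parts.

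**3. Share of the post-dose period.** 62/90 = 68.9%. With the ±1 day visit window, follow-up of 29 days gives 61/90 = 67.8% and follow-up of 27 days gives 63/90 = 70.0%.

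**4. Share of the whole Section 7.3.5 window.** That window starts with study intervention, so its length is (last-dose day − 1) + 90.

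| | Whole window | Uncovered | Share |
|---|---|---|---|
| Part 1 | (85 − 1) + 90 = 174 days | 62 | 35.6% |
| Part 2 | (134 − 1) + 90 = 223 days | 62 | 27.8% |

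**5. Overlap with contraception.** Contraception is required for 30 days or 5 half-lives after the last dose, whichever is longer. That is at least 30 days, which is longer than 28. Any contraception-free day within the 90-day window therefore lies in the uncovered part. The number of such days depends on the human half-life, which the public text does not give. If the half-life is 6 days or less (5 × 6 = 30), there are 60 (days 31 to 90). At 18 days (5 × 18 = 90) there are none.

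**6. What other clauses recover.** The post-study clauses in Section 7.3.1 and Appendix 4 cover SAEs that the investigator happens to learn of and considers related. They do not capture an uncomplicated pregnancy, or an outcome judged unrelated, that begins after the study. Outcome follow-up in Appendix 4 is active and long, but it starts only once a pregnancy has been collected.

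**The case against.** The strongest reply is that Section 7.3.5 governs *when* and Appendix 4 governs *how*. The 90-day sentence is explicit. Appendix 4 does not say that later pregnancies are excluded; its word *only* attaches to subjects who received study intervention. The 28 days is inferred from the End of Study visit and is not written in the appendix. A careful site would apply the 90 days. This stands as a reason to call the loss possible rather than certain. It does not remove the mismatch, because the operative sentences in Appendix 4 describe a shorter period and no scheduled contact delivers the longer one.

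Three stronger readings are tempting, and the documents do not support them:

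- *Two thirds of the stated window is lost.* The window in Section 7.3.5 begins at the start of treatment. Two thirds describes the 90 post-dose days only; of the whole window the share is 36% in Part 1 and 28% in Part 2.
- *Most conceptions would fall in the gap.* Contraception may lapse there, but nothing in the documents gives the timing or rate of conceptions.
- *Pregnancy outcomes after 28 days go unreported.* For any pregnancy that has been collected, Appendix 4 already requires follow-up to outcome well beyond both 28 and 90 days, and reports every termination and every spontaneous abortion.

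It is also fair to say that the practical reach is small. Section 2.3.1.1 describes Cohorts 1-6 as completed, which leaves mainly the 20 planned subjects of Cohort 7, only some of whom could be affected. Neither SAP shows a planned analysis of pregnancies.

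**Conclusion.** The inconsistency is real and modest. For a subject who completes the planned schedule, up to 62 of the 90 post-dose days fall inside Section 7.3.5 and after the period that Appendix 4 describes. This assumes that being in the study ends at the End of Study visit and that extended antibody follow-up does not count as participation. Where a subject stops dosing early or withdraws, the interval differs.

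Table 8 adds a second mismatch: its SAE period closes at 28 days, although Section 7.3.5 makes abnormal pregnancy outcomes SAEs and Appendix 4 follows them much longer. Few events are expected, but each is a safety record in an area of named potential risk. The wording should be corrected; it does not threaten the trial's efficacy conclusions.

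**What to change.** 1. Reconcile Section 7.3.5 and Appendix 4 to one window for *detecting* pregnancies. The simplest way is to replace the phrases "who becomes pregnant while the male subject is in this study" and "who becomes pregnant while participating in this study" in Appendix 4 with the window already stated in Section 7.3.5.
2. Name the contact that delivers the window, such as a phone call at its end for the subjects concerned.
3. Add a note to Table 8 that outcomes of any collected pregnancy, including those that are SAEs, are reported through the Appendix 4 outcome follow-up regardless of the 28-day limit. Do not put a 90-day limit on outcomes. That would cut off, for example, a stillbirth or congenital anomaly from an on-treatment conception, which Appendix 4 now captures.
4. Keep the existing post-study SAE clauses in Section 7.3.1 and Appendix 4.

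The cost is a few sentences in the protocol and one extra contact for the subjects concerned, mainly in Cohort 7.

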7.4. Treatment of Overdose

There is no experience with overdose of BIO89-100 in humans.

For this study, any dose of BIO89-100 greater than the protocol-specified dose will be considered an overdose.

The Sponsor does not recommend specific treatment for an overdose.

In the event of an overdose, the Investigator should:

- Contact the CRO Medical Monitor immediately.
- Closely monitor the subject for any AEs and laboratory abnormalities until study intervention can no longer be detected systemically (at least 30 days).
- Obtain a plasma sample for PK analysis within 2 days from the date of the overdose if requested by the Medical Monitor (determined on a case-by-case basis).
- Document the quantity of the excess dose as well as the incidence of the overdose in the eCRF.

7.5. Pharmacokinetics

Blood samples for analysis of BIO89-100 serum levels will be collected at the timepoints designated in the SoAs (Table 3 for Cohorts 1-4, Table 5 for Cohorts 5-6, and Table 6 for Cohort 7).

Blood samples will be processed for collection of serum fractions for determination of BIO89-100 serum concentrations. Serum samples will be shipped to the bioanalytical laboratory for analysis.

The trough serum BIO89-100 concentrations will be summarized by treatment group and nominal sampling time using descriptive statistics.

Pharmacokinetic parameters calculated by noncompartmental methods from the BIO89-100 serum concentration data will include:

PK Parameter	Cohorts 1-3	Cohorts 4-5
C_{max}	Within 1 st and 5 th dosing intervals	Within 1 st and 3 rd dosing intervals
$AUC_{0-\tau}$	Within 1 st and 5 th dosing intervals	Within 1 st and 3 rd dosing intervals
t_{max}	Within 1 st and 5 th dosing intervals	Within 1 st and 3 rd dosing intervals
$t_{1/2}$	Within 1 st and 5 th dosing intervals	Within 1 st and 3 rd dosing intervals

Additional PK parameters may be calculated if deemed appropriate.

The serum concentration-time data may also be used for population PK modeling with the results reported separately from the clinical study report.

7.6. Pharmacodynamics and Biomarkers

7.6.1. Immunogenicity Assessments

Antibodies to BIO89-100 as well as titer and binding specificity will be evaluated in serum samples collected from all subjects at timepoints designated in the SoAs (Table 2 for Cohorts 1-4, Table 4 for Cohorts 5-6, and Table 6 for Cohort 7). Subjects who test positive [REDACTED]

[REDACTED] More frequent testing (e.g. every month) or testing for a longer period of time may be requested in the event of safety-related concerns. Follow-up testing will not be required where it is established that the subject did not receive BIO89-100. All follow-up results, both positive and negative will be communicated to the sites. A blood sample for ADA assessment will also be collected upon observation of any severe hypersensitivity reaction (e.g., anaphylaxis). Subjects who test positive [REDACTED]

Samples for endogenous FGF21 level will be collected at baseline for all subjects, and at the time of acquisition of the follow-up blood sample(s) for ADA assessment, in [REDACTED]

Serum samples will be screened for antibodies binding to BIO89-100 and the titer of confirmed positive samples will be reported. Other analyses may be performed to verify the stability of antibodies to BIO89-100 and/or further characterize the immunogenicity of BIO89-100.

The detection and characterization of antibodies to BIO89-100 will be performed using a validated assay method under the supervision of the Sponsor. Antibodies may be further characterized and/or evaluated for their ability to neutralize the activity of the study intervention(s). Samples may be stored for a maximum of [REDACTED] (or according to local regulations) following the last subject's last visit for the study at a facility selected by the Sponsor to enable further analysis of immune responses to BIO89-100.

7.6.2. Pharmacodynamics

The following biomarkers/PD parameters will be evaluated at timepoints designated in the SoAs ([Table 2](#) for Cohorts 1-4, [Table 4](#) for Cohorts 5-6, and [Table 6](#) for Cohort 7):

Laboratory Parameters

- Triglycerides
- Non-HDL cholesterol
- HDL-c
- LDL-c
- HbA1c
- HOMA-IR (Part 1 only)
- Liver function tests: ALT, AST
- GGT
- Alkaline phosphatase
- Adiponectin
- Pro-C3 (see Section [7.6.2.4](#))
- Free fatty acids and Adipo-IR (fasting free fatty acids \times fasting insulin; Part 1 only)

[REDACTED]
[REDACTED]
[REDACTED]
[REDACTED]
[REDACTED]
[REDACTED]

Samples may be stored for a maximum of 15 years after the last subject's last visit for the study, at a facility selected by the Sponsor, to enable further analysis of biomarker responses to BIO89-100.

Residual blood samples will be stored for potential future analysis of biomarkers.

Additional information will be available in the study specific laboratory manual.

Other parameters include:

- Imaging measures (Section 7.6.2.5)
 - MRI-PDFF
 - [REDACTED]
 - [REDACTED]
 - [REDACTED]
 - [REDACTED]
 - [REDACTED]

- Anthropomorphic measurements
 - Body weight
 - [REDACTED]
 - [REDACTED]

[REDACTED]

[REDACTED]

[REDACTED]

[REDACTED]

7.6.2.2. Homeostatic Model Assessment for Insulin Resistance (HOMA-IR; Part 1 only)

HOMA-IR is a method used to quantify insulin resistance based on the following formula(s) (Matthews, 1985):

Glucose in mmol/L	Glucose in mg/dL
HOMA-IR = $\frac{\text{Glucose} \times \text{Insulin}}{22.5}$	HOMA-IR = $\frac{\text{Glucose} \times \text{Insulin}}{405}$

[REDACTED]

[REDACTED]

[REDACTED]

7.6.2.4. N-terminal Propeptide of Type III Collagen (Pro-C3)

N-protease cleaved N-terminal propeptide of type 3 procollagen (P3NP) neo-epitope (Pro-C3) is derived from the synthesis of type 3 collagen. Pro-C3 appears to correlate with liver fibrosis stage, fibrosis regression and response to treatment both as a single test and as part of algorithms (Nielsen, 2015; Daniels, 2018; Hansen, 2018).

7.6.2.5. Magnetic Resonance Imaging – Whole Liver Proton Density Fat Fraction (MRI-PDFF)

MRI-PDFF is a noninvasive, quantitative, and accurate measure of liver fat content (imaging-based biomarker) to assess treatment response in NASH clinical studies (Caussy, 2018).

This technology enables post-processing of MRI data into parametric map of PDFF (Antaros Medical, Sweden) to provide accurate and quantitative measures of liver fat.

[REDACTED]

[REDACTED]

[REDACTED]

[REDACTED]

PDFF

The PDFF is determined using a 6 echo gradient echo pulse sequence covering the liver in the axial plane. Analysis is performed by semi-automatic contouring of the liver in every slice avoiding major vessels and bile ducts. The method applies multi-peak lipid spectral models and simultaneous quantification and correction for T2*. The liver fat value (PDFF) is the mean value of all voxels in the identified volume of interest.

For more information, refer to the Imaging Manual.

7.6.3. Exploratory Analyses

A large rectangular area of the page is completely blacked out, indicating redacted content. The redaction is approximately 15 lines high and 85% of the page width wide, starting below the section header and ending above the page footer.

8. STATISTICAL CONSIDERATIONS

This section describes the statistical analysis as foreseen at the time of planning the study. Changes, additions, and further details about the analyses will be described in the statistical analysis plan, if applicable. Any subsequent additional analyses or changes to analyses that may be required will be fully disclosed in the clinical study report. Summaries and analyses will be presented by dose/treatment group for Part 1 and separately for Part 2. Before database lock, final statistical and pharmacokinetic analysis plans containing full details of all planned analyses will be produced. The analyses presented here represent an outline of the intended methodology. Details of the analysis will be described in a Statistical Analysis Plan. All clinical data will be summarized using descriptive statistics: number (n), mean, standard deviation (SD), median, minimum, and maximum for continuous measurements, and counts and percentages for categorical measurements.

